## **3.2 Exclusion Criteria**

1. Diagnosis of cutaneous, paranasal sinus, salivary, or nasopharynx SCC, or diagnosis of neck nodes with unknown primary.
2. Diagnosis of P16/HPV-ISH positive OPSCC.
3. Presence of distant metastatic disease.
4. Prior systemic therapy for current diagnosis of HNSCC.
5. A history of other malignancy  $\leq 2$  years previous with the exception of basal cell or squamous cell carcinoma of the skin which were treated with local resection only or low risk/curatively treated prostate, thyroid, and cervical cancers.
6. Currently receiving any other investigational agents.
7. Treated within the last 7 days prior to Day 1 of protocol therapy with:

- a. Food or drugs that are known to be STRONG CYP3A4 inhibitors (e.g. grapefruit juice, verapamil, ketoconazole, miconazole, itraconazole, erythromycin, clarithromycin, telithromycin, indinavir, ritonavir, nelfinavir, atazanavir, amprenavir, nefazodone, diltiazem, and delavirdine) or inducers (e.g. glucocorticoids, progesterone, rifampin, phenobarbital, St. John's wort) [moderate CYP3A4 inhibitors/inducers are okay]
  - b. Drugs that are known to prolong the QT interval
  - c. Drugs that are proton pump inhibitors
8. A history of allergic reactions attributed to compounds of similar chemical or biologic composition to palbociclib, cisplatin (for Cohort 1), or cetuximab (for Cohort 2).
9. Uncontrolled intercurrent illness including, but not limited to, ongoing or active infection, symptomatic congestive heart failure, unstable angina pectoris, cardiac arrhythmia, or uncontrolled electrolyte disorders that can compound the effects of a QTc-prolonging drug (e.g. hypocalcemia, hypokalemia, hypomagnesemia).
10. History of cirrhosis.
11. History of renal or liver transplant.
12. Pregnant and/or breastfeeding. Women of childbearing potential must have a negative serum pregnancy test within 28 days of study entry. Female patients must be surgically sterile or be postmenopausal, or must agree to use effective contraception during the period of the trial and for at least 90 days after completion of treatment.
13. Known HIV-positivity and on combination antiretroviral therapy because of the potential for pharmacokinetic interactions with palbociclib. In addition, these patients are at increased risk of lethal infections when treated with marrow-suppressive therapy.

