### **5.3.2 Step One Assessments**

1. Between Cycle 2 post-treatment Day 21 – Day 27, tumor response assessment will be performed by radiologic assessment with CT neck (with IV contrast).
2. Between Cycle 2 Days 18-22, office FOE or OR mDLx to document the size and extent of the PTS along with biopsy of the PTS. Core or excisional biopsies of the involved neck nodes is an alternative approach to obtain tumor tissue.
3. Between Cycle 2 Days 18-22 primary disease site photographs.
4. Clinical examination Cycle 1 Days 1, 15, and 22, and Cycle 2 Day 1 and 22.
5. CBC Days 1, 8, 15, and 22 of each cycle.
6. EKG Cycle 2: Day 1.
7. AE assessments weekly for two cycles.
8. Study Lab collection of 3 green top tubes for PBMC at C1D22 and C2D22.

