### **5.3.5 Step Three Assessments**

Step Three will start 16 to 22 weeks after the completion of CRT.

1. Clinical examination Day 1 of each cycle.
2. CBC Day 1 of each cycle.
3. CMP, Mg Day 1 of each cycle.
4. EKG Day 1 of Cycles 1 and 4, and Day 29 of Cycle 6 (EOT).
5. QOL assessment at Cycle 1 Day 1, Cycle 4 Day 1, and Cycle 6 Day 29 (EOT).
6. AE assessments Day 1 of each cycle.
7. Study Lab collection of 3 green top tubes for PBMC at C1D22.
8. Thirty to 45 days after final cycle of adjuvant palbociclib, there will be a clinical examination, CBC, CMP, EKG, and AE assessment.

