## **5.5 General Concomitant Medication and Supportive Care Guidelines**

While taking palbociclib, patients should be instructed to avoid food or drugs that are known strong CYP3A4 inhibitors or inducers (moderate CYP3A4 inhibitors or inducers are okay). Patients should also refrain from the use of proton pump inhibitors; if needed, alternative antacid therapies may be used including H2-receptor antagonists, and locally acting antacids. H2-receptor antagonists should be administered with a staggered dosing regimen (twice daily). The dosing of palbociclib should occur at least 10 hours after the H2-receptor antagonist dose and 2 hours before the H2-receptor antagonist morning dose. Local antacid should be given at least 2 hours before or 2 hours after palbociclib administration.

Patients should receive full supportive care during the study, including transfusion of blood and blood products and treatment with antibiotics, analgesics, erythropoietin, or bisphosphonates when appropriate.

Anti-emetics (such as prochlorperazine, lorazepam, ondansetron, or other 5-HT3 antagonists) may be administered prophylactically in the event of nausea. Anti-diarrheals, such as loperamide, may be administered as needed in the event of diarrhea.

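### QT-prolonging drugs are barred only before Day 1, and no scheduled ECG falls at sustained palbociclib exposure

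*Combined protocol and SAP*

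**What the plan says.** Section 3.2, exclusion 7, opens "Treated within the last 7 days prior to Day 1 of protocol therapy with" and lists three classes: strong CYP3A4 inhibitors or inducers, "Drugs that are known to prolong the QT interval" (item 7b), and proton pump inhibitors. Exclusion 9 also keeps out patients with "uncontrolled electrolyte disorders that can compound the effects of a QTc-prolonging drug".

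Section 5.5 governs co-medication on treatment. It continues the first class ("While taking palbociclib, patients should be instructed to avoid food or drugs that are known strong CYP3A4 inhibitors or inducers") and the third ("Patients should also refrain from the use of proton pump inhibitors"). It has no rule on QT-prolonging drugs. The same section allows prophylactic antiemetics and names several.

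Palbociclib is given on Days 1-21 of each 28-day cycle, for two cycles in Step One and six in Step Three (Section 5.2.1). After baseline, the only Step One ECG is "EKG Cycle 2: Day 1" (Section 5.3.2). Step Two has one on Day 1 of chemoradiation or RT (Sections 5.3.3 and 5.3.4). Step Three has "EKG Day 1 of Cycles 1 and 4, and Day 29 of Cycle 6 (EOT") and a further one 30 to 45 days after the final cycle (Section 5.3.5). Step One clinic visits are more frequent than the ECGs: "Clinical examination Cycle 1 Days 1, 15, and 22, and Cycle 2 Day 1 and 22".

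Section 6.1.1 sets the response to new grade 2 or worse QTc prolongation at any time on study: an immediate repeat tracing, no dose change at grade 2, a hold with or without reduction at grade 3, and discontinuation at grade 4. It schedules no ECG of its own.

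**The concern.** The plan treats QT risk as something to control. It limits QTc at entry (Section 3.1), excludes QT drugs and uncontrolled electrolyte disorders, and has a graded QTc dose rule. Two gaps weaken that once dosing starts.

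First, of the three drug classes barred before Day 1, QT-prolonging drugs are the only one not carried into treatment. A patient can be given one on Day 2 without breaching any rule in the text available.

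Second, every scheduled ECG falls either on a day without palbociclib or on Day 1 of a cycle, before the drug has accumulated. If prolongation appears only at sustained exposure, alone or together with a QT drug started after Day 1, no scheduled tracing is placed to see it. The holds and reductions in Section 6.1.1 would then depend on somebody ordering an ECG for another reason. Step One has weekly adverse event assessments, but these include no ECG and could not pick up prolongation without symptoms.

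The stake is patient safety during dosing.

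**Working it through.** **Where the scheduled ECGs fall**

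| ECG | Section | Position relative to palbociclib |
|---|---|---|
| Baseline | 5.3.1 | before any drug |
| Step One C2D1 | 5.3.2 | Day 1, 8 days after last planned dose |
| Step Two Day 1 | 5.3.3, 5.3.4 | no dosing; 8 days after last planned dose (Cohort 1), 15 days (Cohort 2) |
| Step Three C1D1 | 5.3.5 | Day 1, 16-22 weeks after chemoradiation |
| Step Three C4D1 | 5.3.5 | Day 1, 8 days after last planned dose |
| Step Three C6D29 | 5.3.5 | no dosing, 8 days after last planned dose |
| 30-45 days after final cycle | 5.3.5 | no dosing |

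On Days 2-21: 0 of 7. On Day 1: 3 of 7. On days without dosing: 4 of 7. Cycles with a scheduled ECG on Days 2-21: 0 of 8.

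**Drug left at those times**

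Input: mean elimination half-life 26.5 h (Section 8.1.3). Assumption: first-order elimination, so the fraction left after t hours is 2^(-t/26.5), relative to the level at the last dose. The documents give no range for the half-life in the text available, so 20-40 h is assumed as a sensitivity range.

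- Day 21 to Day 29: 8 days = 192 h. 192/26.5 = 7.2 half-lives. 2^-7.2 is about 0.7% (0.1% at 20 h, 3.6% at 40 h).
- Measured instead against the steady-state pre-dose trough, the interval is 168 h and about 1.2% is left (0.3% to 5.4%).
- Cohort 2 RT Day 1: 15 days = 360 h. 360/26.5 = 13.6 half-lives, about 0.01% left.

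Check on the model: the accumulation ratio it implies is 1/(1 - 2^(-24/26.5)) = 2.14, against the stated median of 2.4. That is close enough for this purpose.

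**If a Day 1 ECG is taken after the dose**

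The plan does not fix the order of ECG and dose on these days. Section 8.1.7 puts the ECG first only on pharmacokinetic sampling days, and this schedule has none. A post-dose Day 1 tracing would reflect roughly a first dose. From the Section 8.1.3 table at 125 mg, Day 1 against Day 8:

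- AUC(0-10): 299/724 = 41%.
- Cmax: 51.6/86.2 = 60%.

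These ratios are rough. Patient numbers differ between the two days, and the 100 mg AUC ratio is 332/513 = 65%.

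**The proposed slot, Cycle 1 Day 15**

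After 14 daily doses (336 h), exposure is 1 - 2^(-336/26.5) = 99.98% of steady state. A pre-dose tracing would sit at about 2^(-24/26.5) = 53% of the post-dose level, which is why the ECG should follow the dose.

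**What the move does to the intervals**

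Count study days from C1D1. C2D1 is Day 29, Step Two starts on Day 57, and Cohort 2 RT Day 1 is one week later, Day 64.

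- Cohort 1: 57 - 29 = 28 days now; 57 - 15 = 42 days after the move.
- Cohort 2: 64 - 29 = 35 days now; 64 - 15 = 49 days after the move.

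**The case against.** The strongest reply is that no clinical risk has been shown. The only QT evidence in the text available is one nonclinical statement in Section 8.1.9. Some of the pharmaceutical text was not available, nor was the Investigator's Brochure to which Section 8.1.3 refers, and either might hold clinical QT data that justify a light schedule. The plan admits any QTc below 500 msec and makes no dose change at grade 2, which fits a deliberate choice. This stands as a limit on weight. It does not explain why one of three paired drug restrictions stops at Day 1.

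There are also other controls. Unscheduled ECGs feed directly into Section 6.1.1. A QT drug still being taken could show its own effect on a later Day 1 tracing. Chemistry and magnesium are checked on Day 1 of every Step Three cycle. All of this is true, but none of it is a scheduled tracing at sustained exposure, and in Step One the chemistry panel and magnesium are listed at baseline only.

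Two points about the remedy also stand. Giving up C2D1 removes a real check and leaves Cycle 2 of Step One without a scheduled ECG. And Step Three has six of the eight cycles, with examinations on Day 1 only. An ECG at the next visit after a QT drug is started would usually land on the nearly drug-free slot, so the rule has to be tied to dosing days. Any new restriction must also be squared with the antiemetics that Section 5.5 allows by name.

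A reader might go further and infer that palbociclib is known to prolong QTc in these patients, that the plan cannot detect prolongation at all, or that every Day 1 ECG precedes the dose. The documents support none of these. The evidence shown is nonclinical, unscheduled tracings and Section 6.1.1 remain in force, and the order of ECG and dose on Day 1 is not stated.

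**Conclusion.** The point holds as a gap in safety monitoring. Exclusion 7b lapses at the first dose while its two companion restrictions continue. All 7 scheduled ECGs miss Days 2-21 in all 8 cycles. The only Step One ECG after baseline comes when about 0.7% of the drug remains (0.1% to 3.6% for assumed half-lives of 20 to 40 h). Prolongation confined to sustained exposure would therefore trigger Section 6.1.1 only through an unscheduled tracing.

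The conclusion rests on doses and visits taking place on their planned days and on first-order elimination. The count of ECGs needs neither the half-life nor the exposure ratios.

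The documents give no rate of QTc prolongation, so no number of affected patients can be stated. A reader might suspect that the response rate is compromised; nothing here bears on it. A reader might also take the change below to close the gap throughout. It does not: after it, 7 of 8 cycles still have no routine ECG on Days 2-21, and prolongation from palbociclib alone in Step Three stays uncovered.

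**What to change.** 1. In Section 5.3.2 item 6 and calendar 10.1, move the Step One ECG from Cycle 2 Day 1 to Cycle 1 Day 15, after that day's dose, with time since dose recorded. Day 15 is already an examination and CBC visit.

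2. In Section 5.5, after the proton pump inhibitor sentence, state that drugs covered by exclusion 7b are to be avoided while palbociclib is taken in Steps One and Three. If one is unavoidable, including any antiemetic named in that section that the site classes as QT-prolonging, require an ECG on a palbociclib dosing day while both drugs are being taken, and not merely at the next scheduled visit. Because Day 1 is formally a dosing day, the wording should make clear that a Day 1 tracing does not meet this requirement.

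3. Record as a limit that routine Step Three ECGs still do not sample sustained exposure. Section 6.1.1 needs no change.

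Cost: one ECG is re-timed per patient, with no added routine visit or procedure. The Cycle 2 Day 1 tracing is lost, and the next scheduled ECG comes 42 rather than 28 days later in Cohort 1 (49 rather than 35 in Cohort 2). Keeping both tracings would avoid that, at 24 extra ECGs for 24 patients. Item 2 brings an occasional change of co-medication and an occasional unscheduled ECG, which in Step Three may need a separate visit.

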### **5.3.3 Step Two Cohort 1 Assessments**

Step Two will start the day after Cycle 2 Day 28 of neoadjuvant palbociclib monotherapy.

1. Clinical exam on Days 1, 8, 22, 29, and 36 then biweekly until adequate recovery from CRT toxicities per physician discretion.
2. CBC Days 1, 8, 22, and 29.
3. CMP, Mg Days 1 and 22. BMP, Mg on Days 8 and 29.
4. QOL assessment Days 1 and 36.
5. EKG Day 1.
6. AE assessments on Days 1, 8, 22, 29, and 36 during CRT.
7. Office FOE between 8-10 weeks after completion of CRT.
8. CT neck with IV contrast between 8-10 weeks after completion of CRT.
9. Primary disease site photographs between 8-10 weeks after completion of CRT.
10. FDG-PET/CT between 14-18 weeks after completion of CRT.

### **5.3.4 Step Two Cohort 2 Assessments**

Step Two will start the day after Cycle 2 Day 28 of neoadjuvant palbociclib monotherapy.

1. Clinical exam on day of loading dose of cetuximab, then on RT Days 1, 8, 22, 29, and 36, then biweekly until adequate recovery from CRT toxicities per physician discretion.
2. CBC day of loading dose of cetuximab, then on RT Days 1, 8, 22, and 29.
3. CMP, Mg on day of loading dose of cetuximab, then on RT Days 1 and 22. BMP, Mg on Days 8 and 29.
4. QOL assessment RT Days 1 and 36.
5. EKG on RT Day 1 (Week 2 of cetuximab).

6. AE assessments on day of loading dose of cetuximab, then on RT Days 1, 8, 22, 29, and 36.
7. Office FOE between 8-10 weeks after completion of CRT.
8. CT neck with IV contrast between 8-10 weeks after completion of CRT.
9. Primary disease site photographs between 8-10 weeks after completion of CRT.
10. FDG-PET/CT between 14-18 weeks after completion of CRT.

### **5.3.5 Step Three Assessments**

Step Three will start 16 to 22 weeks after the completion of CRT.

1. Clinical examination Day 1 of each cycle.
2. CBC Day 1 of each cycle.
3. CMP, Mg Day 1 of each cycle.
4. EKG Day 1 of Cycles 1 and 4, and Day 29 of Cycle 6 (EOT).
5. QOL assessment at Cycle 1 Day 1, Cycle 4 Day 1, and Cycle 6 Day 29 (EOT).
6. AE assessments Day 1 of each cycle.
7. Study Lab collection of 3 green top tubes for PBMC at C1D22.
8. Thirty to 45 days after final cycle of adjuvant palbociclib, there will be a clinical examination, CBC, CMP, EKG, and AE assessment.

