## **6.0 DOSE DELAYS/DOSE MODIFICATIONS**

### **6.1 Dose Modifications for Palbociclib (Steps One and Three)**

Patients will be monitored for toxicity and the dose of palbociclib may be adjusted as indicated in the table below. Dose reduction by 1, and if possible, 2 dose levels will be allowed depending on the type and severity of toxicity encountered. Patients requiring more than 2 dose reductions will be discontinued from the study.

Recommended dose reductions for palbociclib are to decrease the current dose by 25 mg. The lowest dose available is 75 mg. Doses may be held as needed for toxicity resolution during a cycle. Doses omitted for toxicity are not replaced or restored within the same cycle (meaning that the cycle remains 28 days regardless of the number of doses of taken).

If a patient experiences toxicity which has not resolved to grade 2 or lower within two weeks (inclusive of the scheduled off-week), treatment with palbociclib should be permanently discontinued.

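### Step Three schedules blood counts only on Day 1 of each palbociclib cycle, so a silent Grade 4 count that recovers by Day 29 does not trigger the section 6.1 hold and dose reduction unless someone orders an unscheduled count

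*Combined protocol and SAP*

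**What the plan says.** Section 6.1 is one set of palbociclib rules for Steps One and Three. Its table takes the worst treatment-related toxicity of the previous cycle. After Grade 4 neutropenia or Grade 4 thrombocytopenia, the drug is held until Grade 2 or lower and resumed one level down. The text adds "Doses may be held as needed for toxicity resolution during a cycle", and for toxicity "which has not resolved to grade 2 or lower within two weeks (inclusive of the scheduled off-week), treatment with palbociclib should be permanently discontinued".

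The two steps that share these rules are monitored differently:

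- Step One (5.3.2): "CBC Days 1, 8, 15, and 22 of each cycle" and "AE assessments weekly for two cycles".
- Step Three (5.3.5): "CBC Day 1 of each cycle" and "AE assessments Day 1 of each cycle". Clinical examination is also on Day 1. Calendar 10.2 agrees, with one CBC mark per Step Three cycle and one at the visit after Step Three.
- After Cycle 6: "Thirty to 45 days after final cycle of adjuvant palbociclib, there will be a clinical examination, CBC, CMP, EKG, and AE assessment".

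The only mid-cycle draw in Step Three is the research sample at Cycle 1 Day 22 (5.3.5, 9.2.1 and footnote 13 of calendar 10.2). No CBC is attached to it. Section 1.4 names neutropenia as the dose-limiting toxicity of palbociclib.

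**The concern.** A rule based on the worst grade in a cycle needs at least one count while grades can be at their worst. In Step Three the only scheduled count that can inform the next dose is taken after the off-week, when recovery is expected. A patient with no fever or other symptoms can have a Grade 4 count mid-cycle, recover, show an acceptable count on Day 1 and continue at full dose. In Step One the same event would lead to a hold and a reduction. The site would have followed the protocol exactly in both cases.

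What is at stake is patient safety and dosing in Step Three, and how its haematological toxicity is described afterwards. Step Three carries most of the planned exposure: 6 × 21 = 126 of 126 + 42 = 168 dosing days, or 75%.

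**Working it through.** The plan states no figure on this point, so there is none to reproduce. The check is a count of scheduled CBCs from the visit lists, followed by a trace of what 6.1 would do.

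**Inputs.** Dosing on Days 1–21 of 28-day cycles, two cycles in Step One and six in Step Three (5.2.1); CBC days from 5.3.2, 5.3.5 and calendar 10.2; mean half-life 26.5 hours (8.1.3); dose step 25 mg (6.1).

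**Scheduled counts.** Day 1 CBCs in Step Three fall on step days 1, 29, 57, 85, 113 and 141.

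| | Step One | Step Three as written | Step Three plus Cycle 1 Day 22 |
|---|---|---|---|
| CBCs during treatment | 2 × 4 = 8 | 6 × 1 = 6 | 7 |
| CBCs on Days 2–28, per cycle | 3 | 0 | 1 in Cycle 1, 0 in Cycles 2–6 |
| Longest interval between on-treatment CBCs | 7 days | 28 days | 21 days in Cycle 1, 28 days later |

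**What a Day 1 count measures.** Day 1 is Day 29 of the previous cycle, so it falls 29 − 21 = 8 days after the last dose. That is 8 × 24 / 26.5 = 7.2 half-lives. Assuming first-order elimination, 0.5^7.2, or about 0.7%, of the drug remains. It is a recovery count.

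**After Cycle 6.** Cycle 6 ends on step day 168 and its last dose is on day 161. The next CBC is on day 198 to 213. That is 57 to 72 days after the Cycle 6 Day 1 count and 37 to 52 days after the last dose. No palbociclib dose follows, so this gap affects only what is recorded.

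**Tracing the rule for a Grade 4 count on Day 15 with no symptoms.**

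1. *Step One.* It is seen on Day 15. Dosing is held and resumes at 125 − 25 = 100 mg.
2. *Step Three, Grade 2 or lower by Day 29.* It is on no scheduled CBC. No row of the table is met, and 125 mg continues unless an unscheduled count was done.
3. *Step Three, still Grade 4 on Day 29.* It is seen, held and reduced. Only its onset date is missing.
4. *Step Three, Grade 3 without fever or infection on Day 29.* A low count is seen, but not as Grade 4, and the table has no row for uncomplicated Grade 3 neutropenia. Only the general two-week sentence could apply.

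**What a Cycle 1 Day 22 count adds.** In case 2 it catches the event if the count is still Grade 4 on Day 22, and Cycle 2 then starts at 100 mg. The seven doses on Days 15–21 have already been given. A two-week clock started on Day 22 runs to Day 36; from the true onset on Day 15 it would have ended on Day 29.

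**Upper limit on extra dose.** If the event occurs in Cycle 1, is never seen, and no other reason for reduction arises, Cycles 2–6 run at 125 instead of 100 mg: 5 × 21 × 25 = 2,625 mg, or 13,125 against 10,500 mg.

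**The case against.** The strongest reply is that Step Three monitoring may be lighter by design. Every patient is first scheduled for two cycles at the same dose with eight counts, so poor tolerance should largely have shown itself. Adverse events are also not confined to Day 1: section 7.0 tracks them from start of treatment to 30 days after its last day, section 12.1 requires all to be captured, section 11 has serious toxicities monitored continually, and the diary in Appendix B invites patients to record side effects. Unscheduled counts are always possible.

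Much of this stands. It narrows the gap to a count that is low, transient and without symptoms, because such an event gives no prompt for an unscheduled CBC. The argument from Step One is weaker than it looks. Chemoradiation intervenes, Step Three is three times as long, and section 5.2.1 and the calendar both state 125 mg for it. I found no text carrying a Step One reduction forward. The numerical safety rule in 14.7 concerns delay in starting chemoradiation, so it does not protect Step Three.

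A reader might infer that 6.1 cannot be applied in Step Three at all. The documents do not support that. Non-haematological toxicity, Grade 3 neutropenia with fever or infection, delay of more than a week and failure to deliver 80% of the dose can all be picked up from symptoms, the diary and Day 1 review.

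**Conclusion.** The gap is real but narrow. Followed exactly, the plan takes no scheduled count in Step Three that could show a silent Grade 4 neutropenia or thrombocytopenia which recovers to Grade 2 or lower by Day 29. The hold-and-reduce row then depends on an unscheduled count. This follows directly from the visit lists and needs no assumption beyond adherence to them.

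Its frequency cannot be estimated. The text reviewed, which lacked parts of the prior-trial and pharmaceutical sections, gives no Grade 4 rate on palbociclib alone and no neutrophil recovery time. The 2,625 mg figure is therefore a worst case for one undetected Cycle 1 event. It should not be read as an expected excess.

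Two other stronger readings should be resisted. One is that the two-week discontinuation rule fails and leaves patients dosed unchecked: a Grade 4 count still present on Day 29 is held and reduced, and what is lost is the onset date. The other is that a planned analysis is compromised: the primary endpoint is read at the end of Step One, and section 11 asks for toxicities by cohort, with no comparison by step. The consequence for reporting is that worst-grade haematology in Step Three is a lower bound.

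This is a worthwhile, inexpensive safety improvement. It does not threaten the trial's conclusions.

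**What to change.** In 5.3.5 and the CBC row of calendar 10.2, add a CBC at Step Three Cycle 1 Day 22, taken with the research blood already scheduled that day. A low count late in Cycle 1 can then inform the Cycle 2 dose. The cost is one extra tube per patient, no new visit, and probably some additional dose reductions. Its limits should be acknowledged: it allows no hold within the cycle, does not date an onset on Day 15 and leaves Cycles 2–5 as they are.

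Two further options are for the sponsor to weigh:

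- **Day 15 CBC in Cycles 1 and 2.** This would allow a hold within those cycles, but it needs new visits. Step One counts from Days 8 to 22 can inform the choice, with the caution that Step Three marrow has been through chemoradiation.
- **Cycle 6 Day 29 CBC.** The end-of-treatment EKG is already placed there ("EKG Day 1 of Cycles 1 and 4, and Day 29 of Cycle 6 (EOT"). It would improve adverse-event capture only, since no dose follows.

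If Step Three haematology is reported, describe it as Day 1 (off-week) counts and as a lower bound on worst grade. This costs nothing.
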